3.2.3 Patient reported Harvey-Bradshaw Index

The patient reported Harvey-Bradshaw Index (HBI) is composed of 4 parameters:

1. General well-being (0=Very well, 1=Slightly below Par, 2=Poor, 3=Very poor, 4=Terrible)
2. Abdominal pain (0=None, 1=Mild, 2=Moderate, 3=Severe)
3. Number of liquid stools per day
4. Complications [1 per item: Joint pain (Arthralgia), Eye inflammation (Uveitis), Red nodules on skin (Erythema Nodosum), Canker sores (Aphthous ulcers), Skin wound/ulcers (Pyoderma Gangrenosum), Tear in skin of anal area (Anal fissure), Fluid or pus drainage from anal area (New fistula), and Abscess

Note for #3 that if a patient is using a colostomy bag, the number of times per day the bag is emptied is counted instead.

The use of eCRFs in this registry will allow the total score to be computed and, therefore, not

require the patients to compute the total HBI score. If any of the first 3 parameters are missing, then the total HBI score will be set to missing. Otherwise, the total will be the sum of available data.

In cases where HBI is collected multiple times in the same visit a worst case approach will be taken.

HBI response, determined based on patient reported HBI total scores, is defined as a drop of at least 3 points from baseline HBI total score.

HBI remission, determined based on patient reported HBI total scores, is defined as an absolute score of 4 points or less.

HBI response, determined based on patient reported HBI total scores, is defined as a drop of at least 3 points from baseline HBI total score.

HBI remission, determined based on patient reported HBI total scores, is defined as an absolute score of 4 points or less.

3.3 Definition of Baseline values

In general Baseline values will be determined from the study entry visit (enrollment visit, screening visit, and Baseline visit used interchangeably).

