2.3.1 Patient Inclusion/Exclusion Criteria

Patients who meet all of the following criteria will be eligible for inclusion into the SECURE Registry:

- Patient (or his/her legally acceptable representative) is able to provide written informed consent to permit collection of data.
- Patient must be 18 years of age or older.
- Patient must have medically documented CD.
- The decision to prescribe Cimzia or other medications has been made by the physician independently of the decision to include the patient in the study.
- Patients participating in randomized, blinded clinical trials for CD or other conditions are not eligible for inclusion into the SECURE registry. Involvement in other registries, where patients follow routine clinical practice, is permitted, however.
- The rules for handling erroneous patient entries are laid out in a separate Analysis Data Reviewers Guide.

Cimzia-treated patients

For a patient to qualify as being treated with Cimzia, they must meet one of the following criteria:

- Patient is receiving treatment with Cimzia for the first time. Patient must receive Cimzia treatment within 2 months of enrollment into the registry.
- Patient is currently receiving treatment with Cimzia for ≤ 12 months. Patients must also receive a Cimzia dose within 2 months following enrollment into the registry.

Comparator patients

Patients enrolled in the comparator group are eligible to participate in the registry if one of the following criteria is fulfilled:

- Patient is switching CD treatments or beginning CD treatment for the first time. Previous Cimzia treatment is prohibited in the comparator group. Patient must receive new CD treatment within 2 months of enrollment into the registry.

- Patient is currently receiving other biologic treatment (excluding Cimzia) for ≤ 12 months. Patient must receive other biologic treatment within 2 months following enrollment into the registry.
- Patient is currently receiving immunosuppressant therapy for ≤ 12 months. Patient must receive immunosuppressant therapy within 2 months following enrollment into the registry.
- Patient is currently receiving systemic steroid therapy for ≤ 12 months. Patient must receive systemic steroid therapy within 2 months following enrollment into the registry.

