4 STATISTICAL/ANALYTICAL ISSUES

4.1 Adjustments for covariates

Conventional multiple regression analysis and propensity score analysis will include (but are not limited to) the following Baseline characteristics in the initial run of the model.

Characteristics that are continuous will remain as such. Categorical variables will use the values in parentheses:

- Age
- Gender (Male, Female)
- Race (American Indian/Alaskan native, Asian, Black, Native Hawaiian/Pacific Islander, White, Other/Mixed)
- Smoking status (Never, Current, Former)
- Other biologic treatment use in the year prior to Baseline (Yes, No)
- Immunosuppressant use in the year prior to Baseline (Yes, No)
- Corticosteroid use in the year prior to Baseline (Yes, No)
- Disease extent (Ileum, Colon, Illeocolon, Upper GI, Ileum + upper GI, Colon + upper GI, Illeocolon + upper GI, Other)
- Diagnosed with fistulas (Yes, No)
- Duration of disease
- Physician assessment of disease severity (Remission, Mild-moderate, Moderate-severe, Severe)
- Number of Crohn's related hospitalizations in the year prior to Baseline
- Number of surgical resections in the year prior to Baseline
- Calendar year of enrollment

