4.5 Examination of subgroups

The primary analysis for acute events will be stratified on incidence/prevalence use (yes/no).

The impact of data from the high accruing study site #849 on key outcomes will be assessed (Clinical site closed due to significant noncompliance; reported to FDA's Division of Scientific Investigations in letter dated 29 April 2020).

If sufficient power exists, further stratification based on duration of prevalent use (e.g., 1-5 months, 6+ months, etc.) may be performed. This is described in more detail in Section [8.1.5](#).

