8.1.2.1 Propensity score estimation

The propensity score represents the probability that a specific patient receives Cimzia conditional on a set of known baseline confounding factors (4). A logistic regression model, with treatment cohort as the dependent variable, will be employed to estimate the conditional distribution of the treatment given the covariates. The predictors in this model are pre-treatment variables believed to be related to the study outcome of interest and are listed in Section 8.1.2 These variables were

selected a priori using a directed acyclic graph (DAG). This approach has the advantage of improving the statistical efficiency of a model. It also minimizes the introduction of bias which may result from more traditional confounder identification and adjustment approaches (5).

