8.2 Statistical analysis of the secondary endpoints

A patient reported HBI, completed by each patient, is included as part of the patient disease assessment. Total HBI score will be summarized by enrollment cohort and actual treatment at Baseline for each time point the assessment was collected. Change from baseline for each post-baseline assessment will also be summarized by enrollment cohort and actual treatment at Baseline.

Summary statistics will be provided for the physician assessment of disease severity by enrollment cohort and actual treatment at Baseline for each time point the assessment was collected as well as for the change from baseline for each post-baseline assessment and actual treatment at Baseline.

Summary statistics will be provided for the patient assessment of disease severity by enrollment cohort and actual treatment at Baseline for each time point the assessment was collected as well as for the change from baseline for each post-baseline assessment. The number and percentage of patients in each patient reported disease severity category (remission, mild-moderate, moderate-severe, severe) will also be presented by enrollment cohort and actual treatment at Baseline for each time point.

The physician reported total HBI score will be summarized by enrollment cohort and actual treatment at Baseline for each time point the assessment was collected. Change from baseline for each post-baseline assessment will also be summarized by enrollment cohort and actual treatment at Baseline.

The number and percentage of patients in HBI remission and HBI response, based on the physician reported HBI total score will be presented at each visit for remission and at each post baseline visit for response. The number of patients at each visit will be used as the denominator for percentage of HBI remission. The number of patients with baseline at each post baseline visit will be used as the denominator for percentage of HBI response. Analyses using actual treatment at Baseline will remove the subject from the summaries after they have switched treatment.

A listing will be provided with the physician reported individual HBI items, HBI remission, and HBI response as well as the total score and assessment of disease severity.

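### Propensity predictors called pre-treatment are entry-visit values, recorded on treatment for patients already treated at entry, and the incident/prevalent split covers acute events only

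*SAP*

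**What the plan says.** - **Baseline.** SAP 3.3: "In general Baseline values will be determined from the study entry visit (enrollment visit, screening visit, and Baseline visit used interchangeably". No separate rule is given for patients already on treatment.
- **Eligibility.** SAP 2.3.1 admits new starters and also continuing users. For Cimzia: "Patient is currently receiving treatment with Cimzia for ≤ 12 months". For the comparator: "Patient is currently receiving other biologic treatment (excluding Cimzia) for ≤ 12 months", with the same limit for immunosuppressants and systemic steroids.
- **Predictors.** SAP 8.1.2.1: "The predictors in this model are pre-treatment variables believed to be related to the study outcome of interest". The lists in 4.1 and 8.1.2 include physician-rated severity, and Crohn's hospitalisations and resections in the year before Baseline. SAP 8.1.2.3 matches on a score built from them, and 8.1.5 uses the same covariates in the conventional regressions.
- **Incident and prevalent use.** SAP 4.5: "The primary analysis for acute events will be stratified on incidence/prevalence use (yes/no". SAP 8.1.5 repeats this and defines prevalent users as patients receiving treatment before enrollment. Neither covariate list names the flag, and no such split is stated for malignancy or for the matching.
- **HBI.** SAP 8.2: "Change from baseline for each post-baseline assessment will also be summarized by enrollment cohort and actual treatment at Baseline". Response (SAP 3.2.2 and 3.2.3) is a fall of at least 3 points from baseline.

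**The concern.** A propensity score should balance what the patients were like before treatment could act on them. For a patient who enters some months into treatment, severity at entry may already be an effect of the drug. Matching or adjusting on it can leave severity before treatment unbalanced while the balance table in SAP 8.1.2.4, which sees only entry values, looks satisfactory. The SAP recognises that prior use matters, but acts on it in one analysis only. The gap is most relevant to malignancy, which has no stated split. A smaller point is that HBI and severity change tables mix baselines taken before and during treatment.

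**Working it through.** The plan gives no figure on this point to reproduce. The check compares the passages and then illustrates size. All numerical inputs below are assumptions unless a section is named.

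**1. Look-back window.** The share of the prior year spent on treatment is months on treatment / 12. At 3 months it is 3/12 = 25%, at 6 months 50%, and at 12 months 100%. The hospitalisation and resection counts are therefore mixed for most prevalent users and wholly on treatment only at the 12-month limit. Severity is a single reading at entry, so for any prevalent user it is an on-treatment value.

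**2. Hidden severity difference.** Suppose treatment lowers severity by d standard deviations before entry in both cohorts, and entry severity is balanced exactly. The hidden pre-treatment difference is then d × (difference in prevalent share). The SAP's own imbalance limit of 0.2 (8.1.2.4) is reached at 0.5 × 0.40 = 0.20 or 0.8 × 0.25 = 0.20. With equal shares and equal d it is zero.

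**3. Rate ratio with no drug effect.** Assume 50 of every 100 patients in each cohort were severe before treatment, severity at entry is rated mild or severe, and severe disease multiplies the event rate by R = 1.5 to 2. Let f be the prevalent share and i the fraction of severe prevalent users who improve before entry.

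- Improved: n = 50 × f × i. Rated mild at entry: 50 + n. Share of these originally severe: s = n/(50 + n).
- Pairs rated mild: ratio = [1 + (R−1)s₁] / [1 + (R−1)s₀], where 1 is Cimzia and 0 is comparator.
- All pairs: [M(1 + (R−1)s₁) + S·R] / [M(1 + (R−1)s₀) + S·R]. S = 50 − n₁ pairs are rated severe. M is the number of mild pairs, from 50 + n₀ (equal-sized cohorts) to 50 + n₁ (every Cimzia patient matched).

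| Scenario | s₁ | s₀ | M; S | Mild pairs | All pairs |
|---|---|---|---|---|---|
| A. f = 50% in both; i = 50% Cimzia, 30% comparator | 12.5/62.5 = 0.20 | 7.5/57.5 = 0.13 | 57.5-62.5; 37.5 | 1.03-1.06 | 1.02-1.03 |
| B. f = 70% v 30%; same i | 17.5/67.5 = 0.26 | 4.5/54.5 = 0.08 | 54.5-67.5; 32.5 | 1.08-1.16 | 1.05-1.09 |
| C. All Cimzia prevalent (i = 50%), all comparators untreated | 25/75 = 0.33 | 0 | 50-75; 25 | 1.17-1.33 | 1.10-1.20 |

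Worked example, C with R = 2. With M = 50: (50 × 1.333 + 50)/(50 + 50) = 116.7/100 = 1.17. With M = 75: (100 + 50)/(75 + 50) = 1.20. With R = 1.5 the two figures are 95.8/87.5 = 1.10 and 125/112.5 = 1.11. If f and i are the same in both cohorts, s₁ = s₀ and every ratio is 1.

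**4. What remains after accounting for the flag.** In pairs where both patients are prevalent, with i = 50% and 30%: s₁ = 0.33 and s₀ = 15/65 = 0.23. The ratio in mild pairs is 1.167/1.115 = 1.05 (R = 1.5) or 1.333/1.231 = 1.08 (R = 2). Adjustment reduces the problem among prevalent users without removing it.

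**5. HBI.** If the true fall since starting treatment is 4 points, a share f is prevalent and a fraction g of the fall precedes entry, the observed mean change is 4 × (1 − f·g). For f = 25% to 75% this is 3.5 to 2.5 points at g = 0.5, and 3.0 to 1.0 at g = 1. A patient entering with a score of 0 to 2 cannot fall by 3 points.

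**The case against.** **Both cohorts have the same 12-month allowance and both admit new starters, so the effects may cancel.** This stands in part. They cancel if share, duration and effect on severity are alike, but nothing in the plan ensures that. The label in 8.1.2.1 is inaccurate for prevalent users either way.

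**Acute events are already stratified.** This stands for acute events. A reader might set the extreme ratios above against the detectable ratio of 1.5 for serious infections (SAP 2.4) and conclude that this comparison is compromised. The documents do not support that, because serious infection is classed as acute in Table 8.1 and its primary analysis is stratified on this flag. The stratification has limits: the matching in 8.1.2.3 ignores the flag, so a pair can join a prevalent and an incident user, and no balance check within strata is specified. It does not reach malignancy.

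**Other covariates carry information on earlier severity, and the list is open.** Fistulas, disease extent and duration, and prior-year treatments should absorb some of the difference, so a calculation using severity alone probably overstates it. The lists are expressly not exhaustive and the model is built iteratively (8.1.2.3), which permits the flag but does not commit the SAP to it.

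**The HBI tables do what they say.** This largely stands. Change is defined from study entry, the cited sections do not present it as change since starting treatment, and the analyses are descriptive. A split would be a presentational improvement.

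**Conclusion.** The point holds. For prevalent users, entry severity is not pre-treatment, and the look-back counts are partly on treatment. The incident/prevalent flag is absent from the listed propensity and regression covariates, and no split is stated for malignancy.

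The size is unknown, because the documents give no prevalent share, time on treatment or effect on severity by cohort. It is zero if these are equal. On the assumptions above, the null rate ratio is about 1.02-1.06 with equal 50% shares and unequal improvement (1.02-1.03 over all pairs, 1.03-1.06 in mild pairs), and about 1.10-1.20 over all pairs in the extreme case.

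A reader might take 1.17-1.33 from scenario C as the expected bias. That is not supported: it requires every Cimzia patient to be prevalent and every comparator untreated, against eligibility rules that admit both kinds of patient to both cohorts, and it counts only pairs rated mild. Nor do the documents give any figure linking entry severity to malignancy, so no size can be stated for the primary outcome. This is an inexpensive improvement to the plan; it does not show that the comparison is invalid.

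**What to change.** 1. Add incident/prevalent use of the enrollment treatment to the covariates in SAP 4.1 and 8.1.2, and report its balance under 8.1.2.4. State how switchers are classified: 8.1.5 speaks of receiving treatment before enrollment without naming which treatment.
2. Add a sensitivity analysis of the matched and regression comparisons, including malignancy, in incident users only, for whom the entry visit can be pre-treatment.
3. In 8.1.2.1, describe the predictors as entry-visit values that are pre-treatment only for incident users.
4. Optionally, show HBI and severity change, and HBI response, by incident/prevalent use.

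**Cost.** These are SAP wording and extra outputs from a flag the SAP already defines, with no new data. The incident-user analysis will be less precise, and some matches may be lost. Exact matching on the flag is a stricter alternative, but could discard many patients if prevalent shares differ widely, so covariate adjustment with a balance check is the more proportionate change.

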3.4 Protocol deviations

An important deviation is defined as a deviation from the protocol which could potentially have a meaningful impact on the primary outcome of this study, and are defined as follows:

1. Patient did not sign informed consent.
2. Patient did not have medically documented CD.
3. Patient under 18 years (from protocol amendment 3 onwards)
4. Patient participates in a randomized & blinded clinical trial.
5. Cimzia Cohort patient does not receive Cimzia within 2 months after enrollment (Window of 7 days is allowed).
6. Comparison Cohort patient receives Cimzia prior to enrollment.
7. Comparison Cohort patient does not receive comparator treatment within 2 months after enrollment (Window of 7 days is allowed).
8. Patient is enrolled at more than one site.
9. Any other deviation that the study team determines to be an important deviation over the course of the study.

3.5 Analysis sets

3.5.1 Enrolled Set

All Analyses will be performed on the Enrolled Set, defined as all patients enrolled and with an informed consent. Subjects that were enrolled at more than one site were excluded from the Enrolled Set (See Analysis Data Reviewers Guide for details).

3.5.2 Full Analysis Set

All analyses will be conducted on the Full Analysis Set, defined as all patients enrolled in this non-interventional study that meet eligibility requirements. All data captured from enrollment to last completed follow-up (physician or direct-to-patient) will be included.

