3.2 General study level definitions

Any reference to comparator medication is referring to the 3 medication classes in the eligibility criteria (Corticosteroids, Immunosuppressants or treatment with biologics other than Cimzia) only.

[figure not shown]

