15a	No Cimzia	Comparator > Gap > Cimzia	First Malignancy during Gap and Second Malignancy during Cimzia	Comparator	None	Start of Comparator to First Malignancy Start Date	Start of Cimzia to End of Cimzia	Start of Comparator to End of Comparator	Start of Gap to End of Gap	None
15b	Cimzia	Comparator > Gap > Cimzia	First Malignancy during Gap and Second Malignancy during Cimzia	Cimzia	IC to Malignancy Start Date	None	Start of Cimzia to End of Cimzia	Start of Comparator to End of Comparator	Start of Gap to End of Gap	None
16a	No Cimzia	Gap > Cimzia	Malignancy during Gap	Comparator	None	IC to Malignancy Start Date	Start of Cimzia to End of Cimzia	None	IC to End of Gap	None

#	Dosing prior to IC	Dosing during study (IC onwards)	Adverse Event	Treatment AE assigned to	Malignancy Time at Risk		Other AE Time at Risk			
					Cimzia	Comparator	Cimzia	Comparator	Gap	Overlap
16b	Cimzia	Gap > Cimzia	Malignancy during Gap	Cimzia	IC to Malignancy Start Date	None	Start of Cimzia to End of Cimzia	None	IC to End of Gap	None
17a	No Cimzia	Gap > Comparator	Malignancy during Gap	Comparator	None	IC to Malignancy Start Date	None	Start of Comparator to End of Comparator	IC to End of Gap	None
17b	Cimzia	Gap > Comparator	Malignancy during Gap	Cimzia	IC to Malignancy Start Date	None	None	Start of Comparator to End of Comparator	IC to End of Gap	None
18a	No Cimzia	Gap > Cimzia	Other AE during Gap	Gap	Start of Cimzia to EoS	IC to Start of Cimzia	None	None	IC to Other AE start date	None
18b	Cimzia	Gap > Cimzia	Other AE during Gap	Gap	IC to EoS	None	None	None	IC to Other AE start date	None
19a	No Cimzia	Gap only i.e. no evidence of Comparator or Cimzia dosing	Malignancy during Gap	Comparator	None	IC to Malignancy Start Date	None	None	IC to EoS	None

#	Dosing prior to IC	Dosing during study (IC onwards)	Adverse Event	Treatment AE assigned to	Malignancy Time at Risk		Other AE Time at Risk			
					Cimzia	Comparator	Cimzia	Comparator	Gap	Overlap
19b	Cimzia	Gap only i.e. no evidence of Comparator or Cimzia dosing	Malignancy during Gap	Cimzia	IC to Malignancy Start Date	None	None	None	IC to EoS	None
20a	No Cimzia	Gap only i.e. no evidence of Comparator or Cimzia dosing	Other AE during Gap	Gap	None	IC to EoS	None	None	IC to Start of Other AE start date	None
20b	Cimzia	Gap only i.e. no evidence of Comparator or Cimzia dosing	Other AE during Gap	Gap	IC to EoS	None	None	None	IC to Start of Other AE start date	None

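### Full Analysis Set membership depends on a dose received after enrollment, so a patient whose early event prevents further Cimzia can leave the set with that event; the effect is small and its direction is not shown

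*SAP*

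**What the plan says.** SAP 3.5.2 describes the FAS as "defined as all patients enrolled in this non-interventional study that meet eligibility requirements" and exempts no eligibility item. Protocol 6.4 defines the analysis population in the same terms.

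The criteria in SAP 2.3.1 look forward from enrollment in both cohorts:

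- Cimzia, first-time users: "Patient must receive Cimzia treatment within 2 months of enrollment into the registry".
- Cimzia, current users of up to 12 months: "Patients must also receive a Cimzia dose within 2 months following enrollment into the registry".
- Comparator, switching or starting: "Patient must receive new CD treatment within 2 months of enrollment into the registry".
- Comparator, current biologic users: "Patient must receive other biologic treatment within 2 months following enrollment into the registry". Immunosuppressant and steroid users have parallel rules. One criterion is enough, and previous Cimzia is not allowed.

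SAP 3.4 makes a missed dose an important deviation in either cohort, with a 7-day allowance. Item 5 requires Cimzia itself. Item 7 applies when a "Comparison Cohort patient does not receive comparator treatment within 2 months after enrollment". Section 3.2 explains the term: "Any reference to comparator medication is referring to the 3 medication classes in the eligibility criteria", namely corticosteroids, immunosuppressants and biologics other than Cimzia.

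On which set is used, SAP 3.5.1 and 3.5.2 each claim all analyses. SAP 12.5 puts the FAS first and adds the Enrolled Set, which has no dose condition. SAP 3.5.3 draws the Propensity Score Set from the Enrolled Set.

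**The concern.** An analysis set for a safety comparison should be fixed by what is known when follow-up starts. If membership waits on a later dose, an event that prevents the dose also removes the patient. The patient's later follow-up goes too, so the loss is not confined to the first two months.

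The patients most exposed to this are those dosed with Cimzia before enrollment. Other rules in the SAP treat them as Cimzia patients: section 3.6 places anyone with a dose up to 70 days before baseline in the Cimzia-at-baseline group, and Appendix 1 counts pre-consent Cimzia for malignancy. The same patient can therefore be Cimzia-exposed under one rule and absent from the lead analysis set under another.

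**Working it through.** There is no stated figure to reproduce. The check compares the rules and then bounds the scale.

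**Who is lost.** One Cimzia dose in the window satisfies the rule, so an event that stops Cimzia after that dose stays in the FAS. A patient is lost only if nothing is given in the window. That patient cannot re-enter as a comparator, because previous Cimzia bars it.

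**Rules side by side.**

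| | Cimzia cohort | Comparison cohort |
|---|---|---|
| Window | 2 months + 7 days | 2 months + 7 days |
| Treatment required, SAP 2.3.1 | Cimzia | Same class for current users, or a new CD treatment |
| Treatment required, SAP 3.4 | Cimzia | Any of three classes |
| Nothing received in the window | Fails | Fails |

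The difference is product against class. A comparator patient who stops one drug after an event and moves to another can still qualify; a Cimzia patient who does the same cannot.

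**Where the lost events would have counted.** Appendix 1 of the SAP has rows for "Gap only i.e. no evidence of Comparator or Cimzia dosing".

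- Row 19b (Cimzia before consent, malignancy): event and time go to Cimzia.
- Row 20b (Cimzia before consent, other event): malignancy time goes to Cimzia up to end of study, but the acute event goes to Gap.
- Rows 18a and 18b: an acute event before the first Cimzia dose on study also goes to Gap.

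Patients in rows 19b and 20b fail the Cimzia dose rule and cannot be comparators, so they cannot be in a literally read FAS. Rows 19a and 20a (no earlier Cimzia) are less certain, because a new CD treatment might lie outside the three classes.

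**Scale.** Inputs: 1371 Cimzia patients (SAP 2.4, as of March 2017); 8% annual drop-out and 8 years of follow-up (SAP 2.4); 2 months taken as 61 days.

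- Longest window: (61 + 7)/365.25 = 0.186 years.
- Person-years in the window: 1371 × 0.186 = 255 at most.
- Hazard of drop-out: λ = −ln(0.92) = 0.0834.
- Planned Cimzia person-years: 1371 × (1 − 0.92^8)/λ = 1371 × 0.4868/0.0834 = 8,004.
- Share: 255/8,004 = 3.2%.

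The 8,004 assumes that everyone could be followed for 8 years. SAP 2.3 ends the study on 28 August 2020, so later enrollees could not be, and the true share is higher. In the extreme case that all 1371 enrolled in March 2017 (41 months): 1371 × (1 − 0.92^(41/12))/λ = 4,076 person-years, a share of 6.3%.

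**Events in the window.** The documents give no early event rate, no share of patients already exposed at enrollment, and no time to the next dose. Assuming each, expected events = 1371 × share × days/365.25 × rate/100:

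| Days to first dose after enrollment | Rate per 100 p-y | 25% at risk of removal | 50% | 100% |
|---|---|---|---|---|
| 14 | 1 | 0.1 | 0.3 | 0.5 |
| 14 | 10 | 1.3 | 2.6 | 5.3 |
| 28 | 5 | 1.3 | 2.6 | 5.3 |
| 68 | 1 | 0.6 | 1.3 | 2.6 |
| 68 | 10 | 6.4 | 12.8 | 25.5 |

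The range is about 0.1 to 26 under a constant hazard. These are upper bounds on events lost, since only those that prevent the dose are removed.

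**The case against.** The strongest reply is that the plan already has the safeguard. Every analysis is also run on the Enrolled Set, the matched comparison comes from that set, and a difference between the FAS and Enrolled Set results would be visible. This stands, and it is the main reason the point is modest. It is not complete. SAP 12.5 gives the FAS the leading place. SAP 3.6 starts study-emergent events at consent, while 8.2.2 starts them at the first dose of any CD drug after enrollment. If 8.2.2 governs, events before that dose drop out of those summaries in the Enrolled Set as well.

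Second, exclusion is inferred. SAP 3.5.2 does not list the items that remove a patient, SAP 5.2 only tabulates and lists important deviations, and some data-handling rules sit in a separate reviewers guide. That is fair; the inference is direct, but the SAP should state the rule.

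Third, the SAP follows Protocol 6.4. That also stands, and a change must be declared as a departure.

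A reader might go further and infer that the rule removes early events mainly from the Cimzia side and so biases the comparison in its favour. The documents do not support that. Comparators also face a dose rule, and the criteria for their current users are class-specific. First-time Cimzia users with an event before dosing were not yet exposed, and many pre-dose acute events would count as Gap. Exclusion removes person-time as well as events. Nor do the documents show that a large share of early events is lost.

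**Conclusion.** The point holds in a limited form. On a literal reading, FAS membership depends on treatment after follow-up has begun, and the set leaves out patients whose malignancies or malignancy time the SAP itself gives to Cimzia. The product-against-class difference means that selection can be somewhat stronger for Cimzia, but neither its direction nor its size can be established.

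The effect on long-term rates should be small: at most about 3% of planned Cimzia person-years fall in the window, or about 6% in the extreme case for the early study end. These figures rest on 8% annual drop-out and the March 2017 cohort size; the event counts rest on assumed rates. For malignancy, the primary outcome, a short window matters little against the long latency assumed in SAP 3.2.1, and all analyses are descriptive. The change is still worth making, because the selection is avoidable at little cost.

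**What to change.** 1. In SAP 3.5.2, judge FAS eligibility only on criteria known at enrollment, and record this as a departure from the Protocol 6.4 wording. Alternatively, name the Enrolled Set as the lead set for the safety comparisons and resolve the overlapping claims in 3.5.1 and 3.5.2.
2. Keep the missed 2-month dose as an important deviation, as SAP 3.4 and 5.2 already provide.
3. Tabulate any patients left out of the FAS, with reasons and events, by cohort.
4. Reconcile the start of study-emergent events between SAP 3.6 and 8.2.2.

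The cost is SAP wording, one changed analysis flag and one table; no new data are needed. The small downside is that the FAS would include some patients who never started the intended drug. The Gap and actual-treatment rules already handle their time.
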